## 13. Safety Monitoring and Reporting

### 13.1. Overview

This section defines the types of safety data that will be collected under this protocol and outlines the procedures for appropriately collecting, grading, recording, and reporting those data. AEs that are classified as serious according to the definition of health authorities must be reported promptly (per Section 12.5.1. Reporting of Serious Adverse Events to DAIT/NIAID). Appropriate notifications will also be made to site investigators, Institutional Review Boards (IRBs), and the FDA.

Information in this section complies with International Council for Harmonisation of Technical Requirements for Pharmaceuticals for Human Use (ICH) Guideline E2A: Clinical Safety Data Management: Definitions and Standards for Expedited Reporting, ICH Guideline E-6: Guideline for Good Clinical Practice, 21CFR Parts 312 and 320, and applies the standards set forth in the FDA Guidance for Industry Toxicity Grading Scale for Healthy Adult and Adolescent Volunteers Enrolled in Preventive Vaccine Clinical Trials (September 2007). Refer to [Appendix 4: Tables for Clinical and Laboratory Abnormalities](#).

### 13.2. Definitions

#### 13.2.1. Adverse Event (AE)

An AE is any untoward medical occurrence associated with the use of an intervention in humans, whether or not considered intervention-related (21 CFR 312.32(a)).[19]

The investigator must report adverse events regardless of relationship to study therapy regimen or study mandated procedures.

For this study, an adverse event will include the following associated with the vaccinations/placebo administration or procedures:

- **Vaccine or placebo administration:**
  - All AEs occurring after vaccination/placebo administration and within 7 days after the last dose of vaccine or placebo
  - All solicited local reactions, with the exception of injection site reactions of erythema/redness and induration/swelling measuring <2.5 cm, will be reported as AEs.

- **Study mandated procedures:**

Events related to the following procedures will be considered AEs, with the exception of:

**Blood Draw**

- Bruising at the puncture site less than 2 cm diameter
- Bleeding from the puncture site lasting less than 30 minutes
- Induration/swelling at the puncture site less than 2 cm diameter

**Nasal Swab Collection**

- Bleeding of the nose lasting less than 5 minutes

**13.2.1.1 Suspected Adverse Reaction (SAR)**

Any adverse event for which there is a reasonable possibility that the SARS-CoV-2 vaccine caused the adverse event. For the purposes of safety reporting, 'reasonable possibility' means there is evidence to suggest a causal relationship between the vaccine and the adverse event. A suspected adverse reaction implies a lesser degree of certainty about causality than adverse reaction, which means any adverse event caused by a drug (21 CFR 312.32(a)).

**13.2.2. Solicited and Unsolicited Adverse Events**

For the purposes of this study, the following specific local and systemic reactogenicity events, as well as symptoms of a potential allergic reaction, will be solicited from the participant for 7 days post-vaccination, inclusive of the vaccination/placebo administration day. Refer to [Section 8.2 Enrollment Visit \(Day 1\)](#) and [Section 9.2 Enrollment Visit \(Day 1\)](#).

- Solicited local reactions at the injection site will include erythema/redness, swelling/induration (hardness), and pain.
- Solicited systemic reactions will include fever (assessed as daily oral temperature), myalgia, arthralgia, fatigue, headache, nausea, vomiting, diarrhea, and chills.
- Solicited symptoms related to a potential allergic reaction will include the following:
  - Skin: hives, swelling other than injection site, itching, redness other than injection site, rash
  - Respiratory: wheezing, shortness of breath, coughing, tightness in the throat or chest, sneezing, nasal stuffiness or congestion
  - Gastrointestinal: trouble swallowing, abdominal cramps, diarrhea, nausea, vomiting
  - Dizziness or lightheadedness

All other AEs reported by the participant during the study will be defined as unsolicited AEs.

**13.2.3. Unexpected Adverse Event**

An adverse event or suspected adverse reaction is considered "unexpected" if it is not listed in the Pfizer-BioNTech COVID-19 Vaccine Full FDA EUA Prescribing Information or Moderna COVID-19 Vaccine Full FDA EUA Prescribing Information or is not listed at the specificity, severity or rate of occurrence that has been observed.[9, 13]

**13.2.4. Serious Adverse Event (SAE)**

An adverse event or suspected adverse reaction is considered "serious" if, in the view of either the investigator or DAIT/NIAID Medical Monitor, it results in any of the following outcomes (21 CFR 312.32(a)):

1. Death.
2. A life-threatening event: An AE or SAR is considered “life-threatening” if, in the view of either the investigator or DAIT/NIAID Medical Monitor, its occurrence places the subject at immediate risk of death. It does not include an AE or SAR that, had it occurred in a more severe form, might have caused death.
3. Inpatient hospitalization or prolongation of existing hospitalization.
4. Persistent or significant incapacity or substantial disruption of the ability to conduct normal life functions.
5. Congenital anomaly or birth defect.
6. Important medical events that may not result in death, be life threatening, or require hospitalization may be considered serious when, based upon appropriate medical judgment, they may jeopardize the subject and may require medical or surgical intervention to prevent one of the outcomes listed above.

Elective hospitalizations are not to be reported as an SAE unless hospitalization is prolonged due to complications.

### 13.3. Grading and Attribution of Adverse Events

#### 13.3.1. Grading Criteria

##### 13.3.1.1. Grading of Adverse Events Other than Systemic Allergic Reactions

The study sites will grade the severity of non-allergic adverse events experienced by the study participants according to the criteria set forth in the FDA Guidance for Industry Toxicity Grading Scale for Healthy Adult and Adolescent Volunteers Enrolled in Preventive Vaccine Clinical Trials (September 2007); hereafter, referred to as the FDA Toxicity Grading Scale.

Adverse events will be graded on a scale from 1 to 5 according to the following standards in the FDA Toxicity Grading Scale ([Appendix 4: Tables for Clinical and Laboratory Abnormalities](#)):

- Grade 1 = Mild
- Grade 2 = Moderate
- Grade 3 = Severe
- Grade 4 = Life-threatening
- Grade 5 = Death

Events grade 1 or higher will be recorded on the appropriate AE eCRF for this study.

For grading an abnormal value or result of a clinical or laboratory evaluation (including, but not limited to, a radiograph, an ultrasound, an electrocardiogram etc.), a treatment-emergent adverse event is defined as an increase in grade from baseline or from the last post-baseline value that doesn't meet grading criteria. Changes in grade from screening to administration of the first dose of vaccine/placebo will also be recorded as adverse events, but are not treatment-emergent. If a specific event or result from a given clinical or laboratory evaluation is not included in the FDA Toxicity Grading Scale, then an abnormal result would be considered an adverse event if changes in therapy or monitoring are implemented as a result of the event/result.

### 13.3.1.2. Grading of Systemic Allergic Reactions

The investigator will grade severity of systemic allergic reactions on a scale of 1 to 5 according to criteria set forth in the CoFAR Grading Scale modified for use in adults only ([Appendix 1: CoFAR Grading Scale](#)).

### 13.3.2. Attribution Definitions

The relationship, or attribution, of an adverse event to the vaccine/placebo or study procedure(s) will initially be determined by the site investigator and recorded on the appropriate AE eCRF. Final determination of attribution for safety reporting will be determined by the DAIT/NIAID Medical Monitor. The relationship of an adverse event to the vaccine/placebo or study procedures will be determined using the descriptors and definitions provided in [Table 13.3.2](#).

**Table 13.3.2. Attribution of Adverse Events**

Code	Descriptor	Relationship (to vaccine/placebo or study procedures: blood draw or nasal swab collection)
NOT RELATED CATEGORY		
1	Not Related	The adverse event is clearly not related: there is insufficient evidence to suggest a causal relationship.
RELATED CATEGORIES		
2	Possibly Related	The adverse event has a reasonable possibility to be related; there is evidence to suggest a causal relationship.
3	Related	The adverse event is clearly related.

## 13.4. Collection and Recording of Adverse Events

### 13.4.1. Collection Period

Adverse events will be collected from the time of consent, until a participant completes study participation or until 7 days after their last vaccine dose after he/she prematurely withdraws (without withdrawing consent) or is withdrawn from the study if the participant received study treatment (vaccine or placebo).

AEs will be recorded during the periods defined below.

- **Solicited AEs:** Those occurring within 7 days of each injection (vaccine or placebo), inclusive of the injection day
- **Unsolicited AEs:** Those occurring from the time of consent through study participation

### 13.4.2. Collecting Adverse Events

Adverse events (including SAEs) may be discovered through any of these methods:

- Observing the participant
- Interviewing the participant [e.g., using a checklist, structured questioning, diary, etc.]
- Receiving an unsolicited complaint from the participant

- In addition, an abnormal value or result from a clinical or laboratory evaluation can also indicate an adverse event, as defined in [Section 13.3 Grading and Attribution of Adverse Events](#).

### 13.4.3. Recording Adverse Events

Throughout the study, the investigator will record adverse events and serious adverse events as described previously (Section 12.2 Definitions) on the appropriate AE/SAE eCRF regardless of the relationship to study vaccine/placebo or study procedure.

Once recorded, an AE/SAE will be followed until it resolves with or without sequelae, or the AE/SAE stabilizes, or until the end of study participation, or until 7 days after the participant's last vaccine dose if the participant prematurely withdraws (without withdrawing consent) or is withdrawn from the study, whichever occurs first. Monitoring of a pregnant participant shall continue until the conclusion of the pregnancy.

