If a participant has a Grade 1, per [CoFAR Grading Scale](#), systemic allergic reaction with no evidence of systemic mast cell activation to the first dose of either the Pfizer-BioNTech COVID-19 Vaccine or Moderna COVID-19 Vaccine or if the Grade 1 systemic allergic reaction takes place after the participant has left the vaccination clinic and no tryptase measurements are available, he/she will receive counseling by a study physician and will be allowed to receive a second dose if he/she so chooses.

[figure not shown]
Because the placebo will consist of a normal saline injection, a reaction to placebo will not require termination from subsequent active vaccination, if the participant is willing to proceed following counseling.

If a participant becomes pregnant between the first and second doses of vaccine, she will receive counseling by a study physician and will be allowed to receive a second dose if she so chooses.

Vaccinated participants (placebo and active) will be followed for at least 7 days after their last dose.

Randomized and vaccinated participants will complete study participation in approximately 29 days if vaccinated with the Pfizer-BioNTech COVID-19 Vaccine or 36 days if vaccinated with the Moderna COVID-19 Vaccine. Participants enrolled under protocol versions 1.0 - 4.0 will complete participation in approximately 50 or 64 days if administered placebo before the two doses of Pfizer-BioNTech COVID-19 Vaccine or Moderna COVID-19 Vaccine, respectively, and participants enrolled under protocol versions 5.0 -8.0 will complete participation in approximately 36 or 43 days, respectively, if they receive placebo first.

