## 5. Known and Potential Risks and Benefits to Participants

### 5.1. Risks of Investigational Product as cited in the Full FDA EUA Prescribing Information and/or Package Insert

Adverse reactions following the Pfizer-BioNTech COVID-19 Vaccine that have been reported in clinical trials include injection site pain, fatigue, headache, muscle pain, chills, joint pain, fever, injection site swelling, injection site redness, nausea, malaise, and lymphadenopathy.[13] Severe allergic reactions, including anaphylaxis, other hypersensitivity reactions (e.g., rash, pruritus, urticaria, angioedema), myocarditis, pericarditis, diarrhea, vomiting, and pain in extremity (arm) have been reported following the Pfizer-BioNTech COVID-19 Vaccine during mass vaccination outside of clinical trials.

In a clinical study in children 5 through 11 years of age who received Pfizer-BioNTech COVID-19 Vaccine containing 10 mcg of a nucleoside-modified messenger RNA encoding the viral spike (S) glycoprotein of SARS-CoV-2 (10 mcg modRNA), adverse reactions following administration of any primary series dose included pain at the injection site (84.3%), fatigue (51.7%), headache (38.2%), injection site redness (26.4%), injection site swelling (20.4%), muscle pain (17.5%), chills (12.4%), fever (8.3%), joint pain (7.6%), lymphadenopathy (0.9%), nausea (0.4%), rash (0.3%), malaise (0.1%), and decreased appetite (0.1%).

Following FDA authorization of the Pfizer-BioNTech COVID-19 Vaccine for individuals 12 years of age and older, severe allergic reactions, including anaphylaxis, have been reported outside of clinical trials. Myocarditis and pericarditis have also been reported.

Adverse reactions reported in a clinical trial following administration of the Moderna COVID-19 Vaccine include pain at the injection site, fatigue, headache, myalgia, arthralgia, chills, nausea/vomiting, axillary swelling/tenderness, fever, swelling at the injection site, and erythema at the injection site.[9] Severe allergic reactions, including anaphylaxis, myocarditis, and pericarditis have been reported during mass vaccination outside of clinical trials.

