### **6.5. Premature Discontinuation of Investigational Agent**

Vaccination will be prematurely discontinued for any participant for any of the following reasons:

- Participant has a CoFAR Grade 2 or higher systemic allergic reaction regardless of tryptase, or a CoFAR Grade 1 reaction with elevated tryptase [1.2 x baseline plus 2 ng/ml] that is at least possibly related to the first dose of the vaccine. If the systemic allergic reaction took place after the participant has left the vaccination clinic and no tryptase measurements are available, Grade 1 events will not constitute criteria for discontinuation, but counseling by a study physician will be required (see below).
- The investigator believes that it is no longer in the best interest of the participant to receive the second vaccination

In the above cases, the participant will be asked to return for his/her next in clinic study visit during which reactogenicity symptoms will be reviewed (electronic diary review or return and review of paper diary), adverse events (AEs) and concomitant medications will be recorded, and pre-vaccination biospecimens will be obtained per protocol.

Vaccination may be prematurely discontinued for any participant for any of the following reasons:

- If a participant has a Grade 1 (per [CoFAR Grading Scale](#)) systemic allergic reaction with no evidence of systemic mast cell activation to the first dose of either the Pfizer-BioNTech COVID-19 Vaccine or Moderna COVID-19 Vaccine, he/she will receive counseling by a study physician and will be allowed to receive a second dose if he/she so chooses.
- Because the placebo will consist of a normal saline injection, a reaction to placebo will not require termination from subsequent active vaccination, if the participant is willing to proceed following counseling.
- If a participant becomes pregnant between the first and second doses of vaccine, she will receive counseling by a study physician and will be allowed to receive a second dose if she so chooses.

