## **12. Criteria for Participant and Study Completion and Premature Study Termination**

### **12.1. Participant Completion**

Participation will be considered to be complete when the 7-day follow up after the last vaccination is complete.

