8.3. Deaths and Serious Adverse Events

Serious adverse events (SAEs) will be listed and summarized in the same manner described in Section 8.2. Separate displays listing and summarizing death, including time to death and cause of death, will also be created.

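### A serious event or systemic allergic reaction still unresolved and unstable at the final call, about 7 days after the last dose, need not be followed further, so its outcome may be missing

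*Protocol*

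**What the plan says.** Protocol Section 13.4.3 follows a recorded event until it resolves, "or the AE/SAE stabilizes, or until the end of study participation, or until 7 days after" the last vaccine dose for anyone who withdraws or "is withdrawn from the study, whichever occurs first". The earliest of these ends follow-up. The section makes one exception: a pregnant participant is monitored to the end of the pregnancy, as Section 13.6 also requires.

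Section 12.1 fixes the end of participation: "Participation will be considered to be complete when the 7-day follow up after the last vaccination is complete". Section 3.1 says that vaccinated participants "will be followed for at least 7 days after their last dose". Sections 8.6 and 9.6 place the end-of-study telephone call about 7 days after the last vaccination, with a window of 1 day either side. Section 13.4.1 stops adverse event collection at the same point.

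Section 5.1 gives the risks reported for the vaccines outside trials. After severe allergic reactions, it adds: "Myocarditis and pericarditis have also been reported". Section 13.2.4 counts persistent or significant incapacity among the SAE criteria. SAP Section 8.3 plans this output: "Separate displays listing and summarizing death, including time to death and cause of death, will also be created".

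Participants whose vaccination is stopped come under Section 6.5: "the participant will be asked to return for his/her next in clinic study visit during which reactogenicity symptoms will be reviewed". Adverse events are also recorded at that visit. Section 12.4 places these procedures before the participant is withdrawn.

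**The concern.** Because the earliest end point governs, the end of participation is a cap. It applies even when an event is neither resolved nor stable, and the text makes no distinction between a sore arm and an SAE. An SAE that begins a few days after the last dose can reach the final call while still evolving, and from then on no section obliges the site to find out how it ended.

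The trial is meant to tell highly allergic people, and the parents of children from age 5, whether vaccination is safe for them. Few serious events are expected, so each one will carry weight in that message. One reported without its outcome or sequelae is of limited use. The same holds for a death after the final call from an SAE that began before it: the SAP plans to describe time to death and cause of death, but nothing requires that death to be ascertained.

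There is also a conflict of wording. For withdrawn participants the limit is 7 days after the last vaccine dose. Participants stopped after dose 1 are nevertheless asked back for adverse event recording well after that.

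**Working it through.** **1. The length of the cap.** The days come from Protocol Sections 8.4 to 8.6 and 9.4 to 9.6 and the schedules in Appendix 3. Days from dose 2 to the call = call day − dose 2 day. Days from dose 1 to the call = call day − dose 1 day.

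| Arm | Dose 1 | Dose 2 | Call | Dose 2 to call | Dose 1 to call |
|---|---|---|---|---|---|
| Pfizer-BioNTech, no placebo, all versions | 1 | 22 | 29 | 7 | 28 |
| Moderna, no placebo, all versions | 1 | 29 | 36 | 7 | 35 |
| Placebo + Pfizer-BioNTech, versions 1.0–4.0 | 22 | 43 | 50 | 7 | 28 |
| Placebo + Moderna, versions 1.0–4.0 | 29 | 57 | 64 | 7 | 35 |
| Placebo + Pfizer-BioNTech, versions 5.0–8.0 | 8 | 29 | 36 | 7 | 28 |
| Placebo + Moderna, versions 5.0–8.0 | 8 | 36 | 43 | 7 | 35 |

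The protocol's 7 days is reproduced in every arm. The call window makes it 6 to 8.

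**2. What remains for one event.** An event starting d days after the last dose has 7 − d days until the call, or 6 − d to 8 − d with the window:

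- Onset on the day of the dose (d = 0): 7 days (6 to 8).
- Onset on day 5: 2 days (1 to 3).
- Onset on day 7, with the call on time: none.

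An event after dose 1 has up to 28 or 35 days if dose 2 is given on schedule.

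**3. Is there an exemption?** Section 13.4.3 exempts pregnancy only. Section 13.5.1 has the SAE form updated as more detail arrives and sets no end date, but it does not require the site to seek that detail or to follow the event to resolution. Section 13.3.2 assigns attribution and Section 13.5.3 reporting to VAERS; neither prescribes follow-up. No section lifts the cap for an SAE, a systemic allergic reaction, myocarditis or pericarditis.

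**4. Participants stopped after dose 1.** The next clinic visit falls 21 days after dose 1 for Pfizer-BioNTech (22 − 1, 43 − 22, 29 − 8) and 28 days for Moderna (29 − 1, 57 − 29, 36 − 8). If the limit for withdrawn participants is counted from dose 1, it expires 21 − 7 = 14 or 28 − 7 = 21 days before that visit. Section 12.4, however, has the Section 6.5 procedures completed before withdrawal, so the participant is still on study when the visit takes place. The sections disagree on paper, and which of them governs decides whether this interval is covered.

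**The case against.** The strongest reply is that the cap affects little. The endpoints concern immediate reactions, assessed within 90 minutes, or 48 hours for one secondary endpoint. Such reactions have roughly the full week even after dose 2. Stabilization is an end point in its own right, so an event need not be cured to be properly closed. SAE forms stay open to new information. Myocarditis is a listed product risk, not an objective of the trial. All of this stands, and it limits the point to the few events still unstable at the call. It does not supply the missing duty to follow them.

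Several stronger readings are tempting, and the documents do not support them:

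- A reader might infer that outcomes of serious events are generally not captured. Outcomes reached before the cap are captured, and dose 1 events have 4 to 5 weeks when both doses are given.
- A reader might infer that open events are closed with outcome unknown, or that their final cause is lost. No section says so. Final attribution for safety reporting rests with the Medical Monitor and is not tied to the last call.
- A reader might average 7 − d over the week and quote 3.5 days of follow-up. That assumes uniform onset, for which the documents give no basis, and it suits acute allergic reactions badly.
- A reader might infer that adverse event data on dose 1 reactors are definitely lost for 14 or 21 days. The order set in Section 12.4 makes this a wording conflict that sites could read differently.
- A reader might see a contradiction with SAP Section 8.3. That section displays recorded deaths; it does not promise to look for deaths after participation ends.

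**Conclusion.** The point holds in a limited form. The protocol ends required follow-up of an unresolved, unstable SAE or systemic allergic reaction 7 days (6 to 8) after the last dose in every arm, with pregnancy the only exemption. The final outcome of such an event may therefore be missing. The exposure lies mainly with events that arise after the last dose, and it grows the later they start.

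This rests on two assumptions: that Section 13.4.3 is applied as written, with the earliest end point governing, and that the schedule is kept. The documents give no expected number of such events, so no count can be attached; the number is likely to be small. Estimates of the 90-minute primary endpoint, the sample size and the power do not change. It is a gap in safety information that is cheap to close. The mismatch over participants stopped after dose 1 is a separate matter of reconciling text.

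**What to change.** In Section 13.4.3, exempt SAEs and systemic allergic reactions that are unresolved at the end-of-study call from the earliest-end-point rule. Follow them by telephone or medical records to resolution or stabilization, and enter the outcome on the existing form. Related adverse events of Grade 3 or higher could be added. The protocol already accepts follow-up past the last call for pregnancy. Collection of new events need not be lengthened.

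Separately, reconcile the 7-day limit for withdrawn participants in Sections 13.4.1 and 13.4.3, and the completion rule in Section 12.1, with Sections 6.5 and 12.4. The text should state plainly which period of adverse event collection and follow-up applies to a participant stopped after dose 1.

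The cost is protocol wording, a few calls or record requests, and some form updates. The downside is that a few records stay open past the last call. No visit, sample or change to the analysis is needed.
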